Additionally, patients (or patient's legally authorized representative) will be reminded on a monthly basis to report via their ePRO application whether a bleed has occurred and whether treatment for a bleed or treatment to prevent a further bleed has been given. When a bleed occurs, the patient (or patient's legally authorized representative) will be required to report bleed information, including site of bleed, type of bleed, time of each individual bleed (date, time of start and time of end), symptoms of bleed, and treatment for bleed.

Health status will be captured in ePRO via the visual analogue scale (VAS) component of the EQ-5D-5L at baseline, every 3 months and at the end of study.

Physical activity will be measured daily by wearing a fitness tracker continuously during study participation. Patients will be daily reminded to wear the device. A valid day of monitoring is defined as at least 10 wear hours per day. Wear time will be derived though data collected by the fitness tracker.

The reason for the use of coagulation products (e.g., bleeding, prophylaxis, pain, etc.) will be documented by Investigator in source data and reported in the e-CRF. The reason for the use of coagulation products for bleeding treatment, including agent, start time, dose, route of administration, and number of infusions needed to treat the bleed, will be recorded by patients in the ePRO application and will be then transmitted to the eCRF.

Therapy will be recorded by the investigator at baseline visit and it will afterwards be confirmed by the patient in ePRO application. If there are changes to the assigned therapy, the patient will enter therapy variations in ePRO (*e.g.*, dose, frequency, drug name etc.) and data will be then transmitted to the eCRF.

Demographics and results from physical examinations, and vital sign assessments, will only be collected if available from routine clinical practice. No additional diagnostic or monitoring procedures will be applied to the patients outside of routine clinical practice.

Start Date of Study:

The study start date will be the date of the signing of informed consent of the first patient (or caregiver). The planned start date is October 2019.

End of Study:

The end of the study will be the date on which the last patient performs the last visit, this is expected when:

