The caregiver burden will be evaluated on a monthly basis by collecting the following information: i) the working days lost because of disease; ii) the age of their possible early retirement. Therefore, the productivity loss of caregivers will be estimated considering both the sick leaves of caregiver as well as the economic impact of an early retirement. Data of caregiver burden will be annotated in the ePRO application and then transferred in the eCRF.

In computing the burden for caregivers, the human capital approach will be followed (*Drummond et al. 2005*), valuing the amounts of days and hours of sick leaves by the per hour Italian average wage, according to 2012 Eurostat estimation. Moreover, the charge of early retirement will be estimated by valuing the lost gain from retirement contributions of the working years out of the job market according to Eurostat, and the public expenditure because of the early pension's provision based on Italian Social Insurance Agency (INPS - *Istituto Nazionale della Previdenza Sociale*) data set.

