### **2.3.1      Change in sample size.**

The enrolment was interrupted on 30 April 2021 due to difficulties associated with the SARS-COV-2 pandemic that limited the participation of potential patients in the study within the acceptable enrolment period.. Of the anticipated 150 patients, 107 (71.3%) were included in the study. The reduction of the sample size to 107 patients involves a slight reduction in precision, i.e., an increase in the half-width that will be observed to be less than or equal to 20% (instead of 17% reported in the original protocol) of the standard deviation with an 80% probability. Hence, the reduction of the sample size due to the early interruption of the enrolment does not cause a significant deviation from the planned precision of the estimates.

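### The protocol prices caregiver leave from 2019 onwards at a 2012 hourly wage and values early retirement on a different basis, and the SAP contains no costing rule to replace this

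*Protocol*

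**What the plan says.** The costing is in the Caregiver burden paragraphs of Protocol Section 6.4.1. Two items are collected monthly: "i) the working days lost because of disease; ii) the age of their possible early retirement". From these the protocol intends to estimate a productivity loss that takes account of both leave and early retirement.

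For the method, it says "the human capital approach will be followed". For leave, this means "valuing the amounts of days and hours of sick leaves by the per hour Italian average wage, according to 2012 Eurostat estimation". Early retirement is priced from two sources: contributions forgone over the years out of work (Eurostat), and "the public expenditure because of the early pension's provision" (data from the Italian social insurance agency). Neither early-retirement source carries a price year. The paragraphs mention no uprating, common cost year or number of hours per lost day.

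On timing, Protocol Section 6.1.1 says "The planned start date is October 2019" and sets 12 months of observation, extended to at most 18 months for patients who start a newly approved drug between Month 6 and Month 12. SAP Section 2.3.1 reports "The enrolment was interrupted on 30 April 2021".

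SAP Section 4.4.2 analyses the caregiver's days off work (monthly and annualised) and the caregiver's age at possible early retirement. It contains no monetary calculation.

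**The concern.** Three features of the costing rule do not fit together.

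- **Price year.** The unit price belongs to 2012, while the leave it values begins in late 2019.
- **Units.** The price is per hour and the text speaks of hours of leave, but the data are days.
- **Basis.** One approach is named and, for leave, it is applied by pricing lost time at the wage. For early retirement the text turns to contributions and pension outlay. A caregiver who misses days is costed at the wage, while one who stops work is costed through contribution and pension rules.

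At stake is the meaning of any caregiver productivity loss reported from this study. It would carry an old price for one component, and the other component would not measure the same thing.

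**Working it through.** The documents give no wage, cost total, contribution rate or pension amount, so there is no planned figure to reproduce. The check uses the documents' dates plus labelled assumptions.

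**Inputs**
- Wage year: 2012 (Protocol 6.4.1).
- Earliest leave: October 2019, planned (Protocol 6.1.1).
- Last enrolment: 30 April 2021 (SAP 2.3.1).
- Observation: 12 months, at most 18 (Protocol 6.1.1).
- Annual wage growth g: not in the documents; assumed 0, 0.5, 1 and 2%.
- Contributions c and pension p as fractions of the wage: not in the documents; assumed 0.20 to 0.40 and 0.40 to 0.80.

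**1. Age of the price.** The last patient's observation ends about April 2021 + 12 months = April 2022, or + 18 months = October 2022 if prolonged. In calendar years the gap is 2019 − 2012 = 7 to 2022 − 2012 = 10.

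**2. Understatement of leave.** The proportion missed is 1 − (1 + g)^(−y), where y is the age of the price in years.

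| g per year | y = 7 | y = 10 |
|---|---|---|
| 0% | 0% | 0% |
| 0.5% | 3.4% | 4.9% |
| 1% | 6.7% | 9.5% |
| 2% | 12.9% | 18.0% |

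Counting elapsed time from the start of 2012 to October 2019 and October 2022 (7.8 and 10.8 years) changes the 2% row to 14.3% and 19.3%. The conclusion does not depend on which count is used.

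**3. Units.** Value of leave = days lost × hours per lost day × hourly wage. The protocol supplies the first factor as data and the third as a price. The second is not given, so two analysts could obtain different values from the same days.

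**4. Early retirement.** Pricing a lost work-year at the wage, as is done for leave, gives 1.0 wage-year. If the two named items are summed, the plan gives c + p:
- lowest: 0.20 + 0.40 = 0.60
- middle: 0.33 + 0.60 = 0.93
- highest: 0.40 + 0.80 = 1.20

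The range lies on both sides of 1.0, so the direction of any bias is not determined. The result also moves with contribution and pension rules even when the amount of work lost is unchanged.

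**5. Protocol against SAP.** Protocol Section 6.7 says its statistical methods will be detailed in the SAP. The SAP's caregiver analyses (Sections 2.2.1 and 4.4.2) stop at days and age. Section 6.4.1 is therefore the only rule for any cost that might be reported.

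**The case against.** The strongest reply is that no planned analysis produces this cost. The protocol's objectives and secondary variables are days and retirement age, and the SAP reports just those. Because days are reported directly, any reader can reprice them, and an old wage is a single scaling factor. This stands, and it limits the practical effect. It does not remove the defect: the protocol still commits to a costing, and the only rule for it is the one described.

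A reader might infer three stronger points that the documents do not support:

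- **That both components are out of date.** Only the leave wage carries the year 2012. The early-retirement sources are undated.
- **That the two are added into an uninterpretable total.** The text says both are considered and states no sum. Addition is a natural reading, but reporting them side by side would also satisfy it.
- **That caregiver loss is certainly too low.** For leave this needs positive wage growth, which is assumed here; with 0% growth the error is 0%. For early retirement the sign is unknown.

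It is also fair to say that the early-retirement wording is unclear, so the absence of lost earnings is read from what the text lists and not from an explicit exclusion. The textbook cited for the approach is not available to this review. The argument therefore rests on the protocol's own use of the wage for leave, which it does not carry over to early retirement.

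**Conclusion.** The point holds in a limited form. The leave price is about 7 to 10 years older than the leave it values, with no uprating. This understates leave by 0 to about 18% if wages grew by 0 to 2% a year, an assumption from outside the documents. The hourly price cannot be applied reproducibly to days without a conversion. As worded, early retirement is valued on a different basis from leave under one productivity-loss label, so the components are not on one scale. The size and direction of any bias in that part cannot be determined from the documents.

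This is a minor point about a secondary descriptive item. It does not affect the primary physical-activity endpoint, the sample size or any test.

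**What to change.** 1. Value leave at the published average hourly wage for the calendar year in which it was taken, or at one stated price year within the observation period.
2. State the number of hours that a lost working day represents.
3. Value work-years lost to early retirement at the same wage.
4. Report public pension spending separately as a public-budget transfer, not as part of productivity loss.
5. Put this costing into the SAP, or remove it from the protocol if it will not be reported.

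The cost is protocol and SAP wording, a more recent published wage figure and a stated hours convention. No new patient data are needed.

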6.4.2 Data Collected at Study Completion

For patients who complete the observation period, the study completion visit will be documented.

Please see Appendix 2 for the data to be collected at the study completion visit.

6.5 SUBJECT, STUDY AND SITE DISCONTINUATION

6.5.1 Subject Withdrawal

Patients have the right at any time and for any reason to withdraw their consent that their data are collected and used for the study. Reasons for withdrawal from the study may include, but are not limited to, the following:

- Patient withdrawal of consent at any time;
- Any medical condition that the investigator determines may jeopardize the patient's safety
 if he/she continues in the study;

- Investigator determines it is in the best interest of the patient;
- Patient's inability or unwillingness to comply with protocol requirements or noncompliance despite appropriate education measures taken by the clinical site.
- Patient died.
- Patient lost to follow-up.

Patients may elect to withdraw from the physical activity monitoring but continue participation in the remainder of the study. If a patient decides to withdraw only from the physical activity monitoring prematurely, the patient will continue with the follow-up visits as per the study protocol. Every effort should be made to obtain information on subjects who withdraw from the study. The primary reason for withdrawal from the study should be documented on the appropriate CRF page. Subjects will not be followed for any reason after consent has been withdrawn. Patients who withdraw from this part of the study will not be replaced.

6.5.2 Study and Site Discontinuation

The study initiator has the right to terminate this study at any time. Reasons for terminating the study may include, but are not limited to, the following:

Patient enrolment is unsatisfactory.

The Sponsor will notify the physician if the study is placed on hold, or if the Sponsor decides to discontinue the study.

The study initiator has the right to replace a site at any time. Reasons for replacing a site may include, but are not limited to, the following:

- Excessively slow recruitment,
- Poor protocol adherence,
- Inaccurate or incomplete data recording,
- Non-compliance with the Guidelines for Good Pharmacoepidemiological Practices (GPP) or any other pertinent local law or guideline,
- No study activity (i.e., all patients have completed and all obligations have been fulfilled).

6.6 DATA MANAGEMENT

6.6.1 Data Quality Assurance

The contract research organization (CRO) Data Management will identify and implement the most effective data acquisition and management strategy for the clinical trial protocol and deliver datasets which support the protocol objectives. Patient data will be entered into the eCRF and combined with data provided from other sources (e.g., wearable device, ePRO data) in a validated data system.

Clinical data management will be performed in accordance with applicable CRO standards and data cleaning procedures with the objective of removing errors and inconsistencies in the data which would otherwise impact on the analysis and reporting objectives, or the credibility of the Clinical Study Report. Concomitant medications terms will be coded using validated dictionaries.

ePRO data collection will be performed directly by the patients through a dedicated application that runs on the patient's own device (BYOD approach. Physical activity will be measured by wearing a study device (*i.e.*, fitness tracker) in a continuative manner during study participation.

The eCRFs and correction documentation will be maintained in the EDC system audit trail. System backups for data stored at the CRO and records retention for the study data will be consistent with the CRO standard procedures. The CRO will comply with the Sponsor's procedures regarding TMF archiving and record management.

The study data should be verified by the Clinical Research Associate (CRA), *i.e.* the study monitor, with the original data, thereafter all the records and clinical records of the subjects could be accessible. The investigator should allow the access to patient clinical records and the original data should be available for all the study duration. Also the subjects and parents/legal representatives should allow the access to their own clinical records; such condition is cleared and authorized when the subjects supply their authorization for the participation to the clinical study.

6.6.2 Electronic Case Report Forms

Clinical data will be captured using a study specific eCRF using a validated and Code of Federal Regulations (CFR) Part 11 compliant electronic data capture (EDC) system. Sites will receive training and have access to a manual for appropriate eCRF completion.

All eCRFs should be completed by designated trained site staff and reviewed, electronically signed and dated by the Investigator.

At the end of the study, each site will receive their patient's data in an electronic readable format (*i.e.*, PDF format) burned on an adequate media (*e.g.*, CD or DVD). The site will receive a PDF file for each enrolled subject, the file will contain the patient's data and its audit trail. Data files shall be archived with the site study records.

6.6.3 Source Data Documentation

Clinical monitors will perform ongoing source data verification (SDV) as defined in the Trial Monitoring Plan to confirm that protocol data (*i.e.*, source data) entered in the eCRF by authorized site personnel are accurate, complete, and verifiable from source documents.

Source documents (paper or electronic) are those in which patient data are recorded and documented. They include, but are not limited to, hospital records, clinical and office charts, laboratory notes, memoranda, ePRO data transferred in the database, evaluation checklists, recorded data from automated instruments, copies of transcriptions that are certified after verification as being accurate and complete, patient files, and records kept at laboratories, and medico-technical departments involved in the clinical study.

Before study initiation, the types of source documents that contain study-relevant information will be clearly defined in the Trial Monitoring Plan. The Trial Monitoring Plan defines which kind of source data – if available from clinical routine - can be used for documentation into eCRF. No additional source data creation beyond clinical routine is allowed.

Source documents that are required to verify the validity and completeness of data entered in the eCRF must not be obliterated or destroyed and must be retained per the policy for retention of records described in Section 6.8.4.

To facilitate SDV, the physicians and institutions must provide the Sponsor direct access to applicable source documents and reports for trial-related monitoring, Sponsor audits, and EC review. The participating sites must also allow inspection by applicable health authorities.

6.7 STATISTICAL CONSIDERATIONS

The appointed CRO will be responsible for the statistical analysis of the study. All statistical analyses and data processing will be performed using Statistical Analysis Software (SAS), release 9.4 or later, under Windows 7 or Windows 10 Pro operating system.

The statistical methods planned in this study protocol (see below) will be detailed, agreed and approved in a statistical analysis plan (SAP) which will be finalised before database lock.

Descriptive statistics will be provided in summary tables according to the type of the variable. Continuous variables will be summarized by using number of cases, mean, and standard deviation, median, quartiles and range (*i.e.*, minimum and maximum). Categorical variables will be summarized by using frequency and percent distribution.

Populations for analysis

The following populations will be considered for the analysis:

- Enrolled population: all patients for whom the inclusion/exclusion criteria have been verified and met;
- Evaluable population: all enrolled patients with at least 6 valid months of physical activity evaluations during monitoring through the fitness tracker during the study.

Analysis of demographic an disease characteristics will be performed in the Enrolled population. Analysis of primary, secondary and exploratory variables will be performed in the Evaluable population.

Missing data

Imputation methods for missing values will be discussed and detailed in the SAP as deemed appropriate.

6.7.1 Analyses

Primary variables (*i.e.*, daily evaluations of active minutes, steps count, METs) will be analysed over the 12-18 months' observational period by means of descriptive statistics (e.g. weekly/monthly). The 95% confidence interval (CI) of the mean will be also presented.

Moreover, results will be also shown graphically, if deemed necessary.

Analyses of primary variables will be conducted on patients with established valid measurements from the fitness tracker.

A sensitivity analysis could also be performed evaluating the relationship of primary variables with baseline, demographic or other clinically relevant variables, which will be detailed and described in the SAP.

Secondary variables will be summarized by using descriptive statistics as indicated in general methodology section, according to the type of variable analyzed, at any given time point (where applicable). The 95% CI of the mean change could be also presented.

Particularly, the proportion of patients who will meet WHO recommendations for physical activity will be summarized using descriptive statistics and 95% CIs as well.

The same analysis will be performed on active/sedentary patients and severe/moderate patients.

A further exploratory analysis will be performed in patients that will start treatment with any newly approved drugs during the study. An intra-patient comparison will be performed on pre and post treatment start primary and secondary variables evaluations.

Due to the exploratory nature of this study, no adjustment for multiplicity will be made.

6.7.2 Interim and Final Analyses and Timing of Analyses

One interim analysis is planned, when all enrolled patients have completed 6 months of observation, to have a preliminary evaluation of results and to check if any adjustment in terms of number of required patients or in terms of study procedures may be necessary.

Once the study database is considered clean and before database lock, a data review meeting might be performed. During this meeting the study data will be reviewed to identify potential issues and document decisions taken to address them before the database is locked and the analysis of the data starts. Details of this analysis will be provided in the SAP.

A final analysis will be carried out at the end of study, *i.e.* all patients enrolled and followed up (with no limitations in the period of follow-up) will be included in the data analysis.

